## 1. AMENDMENTS FROM PREVIOUS VERSION(S)

Not applicable.

## 2. INTRODUCTION

This document describes the planned statistical analyses for Protocol B7521001. This analysis plan is meant to supplement the study protocol. In this document, any text taken directly from the protocol is italicized. Any deviations from this analysis plan will be described in the Clinical Study Report (CSR).

### 2.1. Study Design

This is a Phase 1, two part, open label, multi-center, single arm, non-randomized, multiple dose, safety, pharmacokinetic and pharmacodynamic study of single agent ADC (PF-06647263) in sequential cohorts of adult patients with advanced solid tumors for whom no standard therapy is available. Successive cohorts of patients will receive doses of ADC (PF-06647263) intravenously on an outpatient basis every 21 days starting at a dose of 0.015 mg/kg.

The proposed doses, schedule(s) and PK timepoints may be reconsidered and amended during the study based on the emerging safety and pharmacokinetic data.

The actual number of patients enrolled will depend upon tolerability of ADC (PF-06647263) and the number of dose levels required to identify the MTD.

Patients will participate in the study for approximately 6 months. This assumes up to 4 weeks of screening, approximately 4 months of treatment, and a follow-up visit within 4 weeks after the last dose for adverse event (AE) and serious adverse event (SAE) collection. Treatment with study drug will continue until disease progression, patient refusal, unacceptable toxicity occurs, or the study is terminated.

This clinical study will include 2 parts. Part 1 will estimate the MTD in dose escalation cohorts in patients with advanced solid tumors for whom no standard therapy is available in order to establish the RP2D. Part 2 will include approximately 30 patients enrolled at the MTD in order to explore benefit from treatment as suggested by preclinical findings and will better define the safety profile at the RP2D. This expansion cohort will include approximately 15 patients with TNBC and 15 patients with OVCA. Additional safety information gathered in Part 2 may be used to modify the dose recommended for future Phase 2 trials.

### 2.2. MTD Determination (Part 1)

A modified toxicity probability interval method (mTPI) targeting a DLT rate of 25% with an equivalence interval (20%-30%) will be utilized in order to estimate MTD. Patients will be enrolled in cohorts of 2 to 4, starting with 0.015 mg/kg for the first cohort. Subsequent dose levels may include a maximum 100% escalation until either the dose is  $\geq 0.060$  mg/kg, a patient experiences a DLT or Grade 2 thrombocytopenia considered related to PF-06647263

after which, dose escalation in subsequent cohorts will follow a modified Fibonacci scheme with maximum dose increases of 67%, 50%, 33%, 33%. Table 1 illustrates the possible dose levels when the Modified Fibonacci scheme is initiated at the 3rd dose level. Intermediate dose levels to further evaluate the safety and/or PK may be evaluated following discussion between Sponsor and Investigator.

	Modified Fibonacci^ scheme starts from dose level 3	Modified Fibonacci^ scheme starts from dose level 2	Modified Fibonacci^ scheme starts from dose level 1
Dose Level	Dose (mg/kg Q3W)	Dose (mg/kg Q3W)	Dose (mg/kg Q3W)
-1	0.01	0.01	0.01
1 (Starting dose)	0.015	0.015	0.015
2	0.030	0.030	0.025
3	0.060	0.050	0.038
4	0.100	0.075	0.050
5	0.150	0.100	0.067
6	0.200	0.134	0.089
7	0.267	0.178	0.119
8		0.238	0.158
9			0.211

The modified toxicity probability interval (mTPI) design uses a Bayesian decision-theoretic framework and a beta/binomial hierarchical model to tailor dose-escalation and de-escalation decisions. These rules are conceptually similar to those used by the 3+3 design and all the dose-escalation decisions for a given trial can be pre-calculated under the mTPI design and presented in a two-way table.

The decision rules to “dose escalate” (E), “no change in dose” (S), “dose de-escalate” (D) or “dose de-escalate, unacceptable toxicity” (U) are described below:

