**Table 1. Decision Rules**

Number	Number of Patients treated at a Dose level											
	DLT	n=2	n=3	n=4	n=5	n=6	n=7	n=8	n=9	n=10	n=11	n=12
0	E	E	E	E	E	E	E	E	E	E	E	E
1	D	S	S	S	E	E	E	E	E	E	E	E
2	U	D	D	S	S	S	S	S	S	S	S	S
3		U	U	D	D	S	S	S	S	S	S	S
4			U	U	U	D	D	D	D	D	D	S
5				U	U	U	U	U	D	D	D	D
6					U	U	U	U	U	U	U	D
7						U	U	U	U	U	U	U

Cohorts of patients could receive doses already tested but a dose that is associated with decision “Dose de-escalate, unacceptable toxicity” cannot be revisited and no more patients should be treated at this dose or higher doses for the remainder of the trial.

A minimum of 9 patients treated at the MTD dose is required to establish such dose as the RP2D. The maximum sample size would be N=70 but actual sample size will depend on the underlying dose toxicity profile and variability in actual data realization. The initial dosing regimen tested in Part 1 will be PF-06647263 administered once every 3 weeks (Q3W) consistent with the pre-clinical toxicity study. Evaluation of a weekly (QW) regimen will be initiated when the first patient treated with the Q3W regimen experiences a DLT or Grade 2 thrombocytopenia related to study treatment. The starting dose of the QW regimen will not exceed one-third of the highest Q3W dose evaluated. Once initiated, the 2 regimens will be evaluated in parallel and independently based on the same dose-escalation criteria as described above.

Dose escalation will stop under any of the following conditions:

1. The maximum sample size has been achieved;
2. At least 9 patients have been accumulated at a dose that is predicted to be the MTD;
3. All doses explored appear to be overly toxic and the MTD cannot be determined.

### 2.3. Part 2

Upon identification of the MTD, approximately 30 patients will be enrolled at the MTD in order to explore benefit from treatment as suggested by preclinical findings and will better define the safety profile at the RP2D. This expansion component aims at evaluating ADC (PF-06647263) at the MTD in two cancer indications:

- a. Previously treated metastatic TNBC which expresses EFNA-4 (15 patients).
- b. Advanced epithelial ovarian cancer, primary peritoneal or fallopian tube cancer (OVCA) which expresses EFNA-4 and which has progressed or relapsed during or within 6 months post most recent therapy with a platinum agent (15 patients).

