## 7.2. Safety Endpoints

### 7.2.1. DLT Definitions

Severity of adverse events will be graded according to NCI CTCAE version 4.03. For the purpose of dose escalation, any of the following adverse events which are not considered related to disease progression, occurring in the first cycle of treatment (Q3W regimen: 21 days or until the patient receives the 2nd infusion if there are treatment delays, QW regimen: 21 days or until the patient receives the 4th infusion if there are treatment delays) will be classified as DLTs:

- Hematologic:
  - Grade 4 neutropenia lasting >7 days.
  - Febrile neutropenia (defined as neutropenia  $\geq$  Grade 3 and a single body temperature  $>38.3^{\circ}\text{C}$  or a sustained temperature of  $\geq 38^{\circ}\text{C}$  for more than one hour).
  - Grade  $\geq 3$  neutropenia with infection.
  - Any grade thrombocytopenia associated with clinically significant or life-threatening bleeding.
  - Grade 4 thrombocytopenia  $\geq 72$  hours or platelets  $\leq 10,000/\text{mm}^3$  regardless of duration.
- Non-hematologic:
  - Grade  $\geq 3$  toxicities, except those that have not been maximally treated (eg, nausea, vomiting, diarrhea).
  - Delay by more than 2 weeks in receiving the next scheduled cycle due to persisting toxicities attributable to PF-06647263.

Grade  $\geq 3$  cytokine release syndrome, infusion related reaction, allergic reaction, or anaphylaxis will not be considered as DLTs but may be a reason for study discontinuation and should be reviewed with Pfizer.

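### Both Part 1 triggers in SAP Section 2.2 name Grade 2 thrombocytopenia without a ≥ sign, so as printed they leave out some worse platelet events that are not DLTs

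*SAP*

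**What the plan says.** Section 2.2 of the SAP uses the same platelet criterion for two Part 1 decisions.

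- **Step size.** Dose increases of up to 100% are allowed until the dose is at least 0.060 mg/kg or "a patient experiences a DLT or Grade 2 thrombocytopenia considered related to PF-06647263". After that, the modified Fibonacci maxima apply (67%, 50%, 33%, 33%).
- **Opening of the QW regimen.** In the text after Table 1 (Decision Rules), evaluation of QW dosing starts when "the first patient treated with the Q3W regimen experiences a DLT or Grade 2 thrombocytopenia related to study treatment".

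Section 7.2.1 defines the platelet DLTs. One is "Any grade thrombocytopenia associated with clinically significant or life-threatening bleeding". The others are Grade 4 lasting at least 72 hours, and platelets at or below 10,000/mm³ for any duration. A delay of more than 2 weeks in the next cycle because of persisting attributable toxicity is also a DLT; it is listed under the non-hematologic items.

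Two statements leave room to go below the maximum step. Section 2.2 says "Intermediate dose levels to further evaluate the safety and/or PK may be evaluated following discussion between Sponsor and Investigator". Section 2.1 says that doses, schedules and PK timepoints "may be reconsidered and amended during the study based on the emerging safety and pharmacokinetic data".

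**The concern.** A trigger meant as an early warning should fire for the named grade and for anything worse. Here the named grade is exactly 2, and the only other limb is a DLT. Between the two lies a group of platelet events that are worse than Grade 2 but fall short of the DLT definition. Followed as printed, the rule reacts to the milder event and is silent on the worse one.

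At stake are the size of the next Q3W dose step at the lowest dose levels and the moment at which QW dosing opens. Thrombocytopenia is the only non-DLT toxicity named in these triggers, so its threshold should leave no doubt.

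**Working it through.** **Is the missing sign an artefact of text extraction?** Probably not. The ≥ sign is present in the same sentence of Section 2.2 (dose ≥0.060 mg/kg) and several times in Section 7.2.1, and the bare Grade 2 wording occurs twice. Section 7.2.1 also writes Grade ≥3 or any grade where a range is meant.

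**Which events fall in the gap?** The table takes a related platelet event in cycle 1 (the DLT window) on the Q3W regimen and applies Section 7.2.1. It then compares the trigger as printed with a Grade ≥2 trigger. Each event is classified by its worst grade. The cycle-delay DLT is taken to cover delays caused by thrombocytopenia.

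| Event | DLT? | Trigger as printed | Trigger with ≥2 |
|---|---|---|---|
| Grade 2 | No | Yes | Yes |
| Grade 3, no bleeding, no delay over 2 weeks | No | **No** | Yes |
| Grade 4 for 48 h, platelets 20,000/mm³, no bleeding, no such delay | No | **No** | Yes |
| Grade 4 for 80 h | Yes | Yes | Yes |
| Grade 3 with clinically significant bleeding | Yes | Yes | Yes |
| Grade 3 with delay over 2 weeks | Yes | Yes | Yes |

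Only the second and third rows differ. They are the whole of the gap.

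**Do the printed dose ladders follow the stated scheme?** Successive ratios from the dose table in Section 2.2 give these increases:

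- Fibonacci from level 3: 100, 100, 66.7, 50.0, 33.3, 33.5%.
- From level 2: 100, 66.7, 50.0, 33.3, 34.0, 32.8, 33.7%.
- From level 1: 66.7, 52.0, 31.6, 34.0, 32.8, 33.7, 32.8, 33.5%.

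These agree with the stated maxima within rounding, so the table can be used to size the effect.

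**Effect on the next Q3W dose ceiling** (ceiling = current dose × 2.00 if not triggered, × 1.67 if triggered):

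- Event at 0.015 mg/kg: 0.015 × 2.00 = 0.030; 0.015 × 1.67 = 0.025. Ratio 0.030/0.025 = 1.20.
- Event at 0.030 mg/kg: 0.030 × 2.00 = 0.060; 0.030 × 1.67 = 0.050. Ratio 0.060/0.050 = 1.20.
- Event at 0.060 mg/kg or above: no difference, because reaching 0.060 mg/kg itself starts the Fibonacci steps.

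**Effect on QW opening.** This trigger has no dose backstop. A missed event at any Q3W dose postpones QW dosing until a later event meets the printed wording.

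**The case against.** The strongest reply is that nobody would apply the text this way. The criterion stands beside a DLT as an early sign of toxicity and reads naturally as a floor. A team that saw related Grade 3 thrombocytopenia would hardly conclude that doubling was still in order. A platelet count may also pass through Grade 2 as it falls or recovers, which could satisfy the literal words. Persistent thrombocytopenia that delays the next cycle by more than 2 weeks is already a DLT. The 100% step is a maximum, and Sections 2.1 and 2.2 allow smaller or reconsidered doses. The protocol, which is not shown, may be worded correctly.

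Most of this stands, and it keeps the point small. It does not make the wording right. The SAP does not say whether a passing Grade 2 value counts. The discretion permits a smaller step but does not require one. The QW opening is written as an event trigger, not as a matter of judgement.

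Some stronger readings are tempting but not supported:

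- **That the QW starting dose becomes unsafe.** If an event at 0.060 mg/kg were missed and the trigger met one level later at 0.100 mg/kg, the QW starting ceiling would move from 0.060/3 = 0.020 to 0.100/3 = 0.033 mg/kg. This is a constructed path. The higher figure still obeys the rule "The starting dose of the QW regimen will not exceed one-third of the highest Q3W dose evaluated", so it shows a later opening and no demonstrated harm.
- **That QW step sizes are affected.** The SAP says "Once initiated, the 2 regimens will be evaluated in parallel and independently based on the same dose-escalation criteria as described above", but not whether the 100% phase starts afresh for QW. That is a separate ambiguity.
- **That the gap widens up the ladder.** The dose-table columns show 0.060 against 0.038 mg/kg at level 3. That contrast assumes that every cohort takes the maximum step and that nothing else fires the trigger at 0.030 mg/kg. The documents give no reason to expect this path.
- **That uncomplicated Grade 3 thrombocytopenia ought to be a DLT.** Leaving it off the list is a design choice and is not in question here.

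**Conclusion.** The point holds as a minor error in the wording of a threshold. As printed, both triggers in Section 2.2 omit related Grade 3 thrombocytopenia, and Grade 4 under 72 hours with platelets above 10,000/mm³, when there is no clinically significant bleeding and no cycle delay of more than 2 weeks. The exception is if a transient Grade 2 value is counted.

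The consequence is confined to a next-dose ceiling 0.005 mg/kg higher after an event at 0.015 mg/kg (0.030 − 0.025), or 0.010 mg/kg higher after one at 0.030 mg/kg (0.060 − 0.050), and to the timing of QW opening. Table 1 acts on DLT counts, so its decisions do not change, nor does any DLT count or the sample size.

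A reader might infer that the sponsor meant to react to Grade 2 and ignore Grade 3. The documents do not support that: nothing in them gives a reason for such a rule, and the intent is almost certainly Grade ≥2. The conclusion rests on the literal text of the SAP and on reading the cycle-delay DLT as covering thrombocytopenia. If that item were limited to non-hematologic toxicity, the gap would be somewhat wider.

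**What to change.** In Section 2.2, write **Grade ≥2 thrombocytopenia** in the sentence that ends the 100% steps and again in the sentence that opens the QW regimen. Make the same change in the protocol if it reads the same. This also removes the question of whether a passing Grade 2 value counts. The cost is one symbol in two sentences, plus any matching protocol text. No patients, procedures or analyses are added, and the DLT list stays as it is.

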**Table 1. Decision Rules**

Number	Number of Patients treated at a Dose level											
	DLT	n=2	n=3	n=4	n=5	n=6	n=7	n=8	n=9	n=10	n=11	n=12
0	E	E	E	E	E	E	E	E	E	E	E	E
1	D	S	S	S	E	E	E	E	E	E	E	E
2	U	D	D	S	S	S	S	S	S	S	S	S
3		U	U	D	D	S	S	S	S	S	S	S
4			U	U	U	D	D	D	D	D	D	S
5				U	U	U	U	U	D	D	D	D
6					U	U	U	U	U	U	U	D
7						U	U	U	U	U	U	U

Cohorts of patients could receive doses already tested but a dose that is associated with decision “Dose de-escalate, unacceptable toxicity” cannot be revisited and no more patients should be treated at this dose or higher doses for the remainder of the trial.

A minimum of 9 patients treated at the MTD dose is required to establish such dose as the RP2D. The maximum sample size would be N=70 but actual sample size will depend on the underlying dose toxicity profile and variability in actual data realization. The initial dosing regimen tested in Part 1 will be PF-06647263 administered once every 3 weeks (Q3W) consistent with the pre-clinical toxicity study. Evaluation of a weekly (QW) regimen will be initiated when the first patient treated with the Q3W regimen experiences a DLT or Grade 2 thrombocytopenia related to study treatment. The starting dose of the QW regimen will not exceed one-third of the highest Q3W dose evaluated. Once initiated, the 2 regimens will be evaluated in parallel and independently based on the same dose-escalation criteria as described above.

Dose escalation will stop under any of the following conditions:

1. The maximum sample size has been achieved;
2. At least 9 patients have been accumulated at a dose that is predicted to be the MTD;
3. All doses explored appear to be overly toxic and the MTD cannot be determined.

### 2.3. Part 2

Upon identification of the MTD, approximately 30 patients will be enrolled at the MTD in order to explore benefit from treatment as suggested by preclinical findings and will better define the safety profile at the RP2D. This expansion component aims at evaluating ADC (PF-06647263) at the MTD in two cancer indications:

- a. Previously treated metastatic TNBC which expresses EFNA-4 (15 patients).
- b. Advanced epithelial ovarian cancer, primary peritoneal or fallopian tube cancer (OVCA) which expresses EFNA-4 and which has progressed or relapsed during or within 6 months post most recent therapy with a platinum agent (15 patients).

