#### **4.2. Statistical Decision Rules**

##### **4.2.1. Part 1**

Decision rules are based on calculating unit probability mass (UPM) of three dosing intervals corresponding to under, proper, and over dosing in terms of toxicity. Specifically, the underdosing interval is defined as  $(0; pT - e1)$ , the over-dosing interval  $(pT + e2)$ , and the proper-dosing interval  $(pT - e1, pT + e2)$ , where  $e1$  and  $e2$  are small fractions. For a target DLT rate of 0.25, the target equivalence interval is  $(0.20, 0.30)$ . The three dosing intervals are associated with three different dose-escalation decisions (Table 1). The under-dosing interval corresponds to a dose escalation (E), over-dosing corresponds to a dose de-escalation (D), and proper-dosing corresponds to remaining at the current dose (S). Given a dosing interval and a probability distribution, the unit probability mass (UPM) is defined as the ratio of the probability of the interval to the length of the interval. Once the safety assessment is complete for Cycle 1, the focus will be on allocation of new subjects to the dose most likely to be an MTD.

The study continues accruing until one of the three stopping conditions below is triggered. The algorithm will stop if any of the following criteria is met:

1. The maximum sample size has been achieved.

2. MTD has been identified with sufficient accuracy: at least 9 patients have been accumulated on a dose that is currently estimated to be the MTD, or
3. All doses explored appear to be overly toxic and the MTD cannot be determined.

Specifically the mTPI approach formalizes stopping rules as follow:

Rule 1 (early termination): if the first dose is too toxic  $\rightarrow \Pr(p_1 > p_T / \text{data}) > \xi$  ;  $\xi = 0.975$

Rule 2 (dose exclusion), if dose=  $i$  is too toxic  $\rightarrow \Pr(p_i > p_T / \text{data}) > \xi$  ;  $\xi = 0.975$   
then exclude doses  $\geq i$

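### The ceiling on the first weekly (QW) dose is tied to the highest Q3W dose evaluated, even if that dose has been declared unacceptably toxic (U); one added clause would close the gap

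*SAP*

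**What the plan says.** All the dosing rules quoted here stand in SAP Section 2.2, in the text under Table 1, unless another section is named.

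- Trigger for the weekly regimen: "Evaluation of a weekly (QW) regimen will be initiated when the first patient treated with the Q3W regimen experiences a DLT or Grade 2 thrombocytopenia". The thrombocytopenia counts only if it is attributed to the study drug.
- Ceiling on its first dose: "The starting dose of the QW regimen will not exceed one-third of the highest Q3W dose evaluated".
- Relation of the two regimens: "Once initiated, the 2 regimens will be evaluated in parallel and independently based on the same dose-escalation criteria as described above".
- Consequence of U: a dose so classified "cannot be revisited and no more patients should be treated at this dose or higher doses for the remainder of the trial". Other tested doses may be given again.
- Section 4.2.1 gives the formal versions. Rule 2 excludes a dose and all higher doses when the posterior probability that its DLT rate exceeds the target is above 0.975. For the lowest dose there is "Rule 1 (early termination): if the first dose is too toxic", with the same threshold.
- Section 7.2.1 sets the weekly DLT window: "QW regimen: 21 days or until the patient receives the". When dosing is late, the end point is infusion number 4. The regular window therefore covers three weekly infusions.

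Section 2.1 allows doses and schedules to be reconsidered on emerging safety data. Section 2.2 allows intermediate doses after discussion between sponsor and investigator.

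**The concern.** The only condition on the reference dose is that it was *evaluated*. The ceiling is therefore the same whether the top Q3W dose was tolerated or was closed for the rest of the trial. The exclusion rules do not help, because one-third of a U dose is a lower dose in mg/kg and they bar only that dose and higher ones. The two regimens are also assessed independently, so the Q3W decision does not carry over.

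QW opens because toxicity has been seen on Q3W, and this ceiling is the only numerical limit the SAP places on the first QW dose. Elsewhere Section 2.2 does react to toxicity: a DLT or related Grade 2 thrombocytopenia ends the 100% steps and starts the modified Fibonacci scheme. The QW ceiling has no such response.

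**Working it through.** **Inputs.** Target and interval from Section 2.2: "targeting a DLT rate of 25% with an equivalence interval (20%-30"%). Cohorts of 2 to 4, the Table 1 decisions and the dose columns are also from Section 2.2; the 0.975 threshold is from Section 4.2.1.

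**Step 1: reproduce the U cells for a single cohort.** The SAP names a beta/binomial model but gives no prior, so Beta(1,1) is assumed. With x DLTs in n patients the posterior is Beta(1+x, 1+n−x), and U requires Pr(p > 0.25) > 0.975.

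| DLTs / n | Pr(p > 0.25) | Table 1 |
|---|---|---|
| 2/2 | 0.984 | U |
| 3/3 | 0.996 | U |
| 3/4 | 0.984 | U |
| 4/4 | 0.999 | U |
| 1/2 | 0.844 | D |
| 2/3 | 0.949 | D |

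These agree with Table 1. One DLT alone gives D (n = 2) or S (n = 3 or 4), so further DLTs are needed before the top dose is U.

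**Step 2: how often a triggering cohort is itself U.** With true DLT rate p:

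- Pr(U) = p² for n = 2; p³ for n = 3; 4p³(1−p) + p⁴ for n = 4.
- Pr(at least one DLT) = 1 − (1−p)ⁿ.

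At p = 0.25:

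- n = 2: 0.0625 / 0.4375 = 14.3%
- n = 3: 0.0156 / 0.5781 = 2.7%
- n = 4: 0.0508 / 0.6836 = 7.4%

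Every U cohort contains a DLT, but QW can also open on Grade 2 thrombocytopenia with no DLT, and Table 1 gives E for such a cohort. Pr(trigger) is therefore at least Pr(at least one DLT), and the ratios above are upper bounds on Pr(U given trigger) for one cohort. Under other assumed rates the bounds are:

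| True DLT rate | n = 2 | n = 3 | n = 4 |
|---|---|---|---|
| 10% (assumed) | 5.3% | 0.4% | 1.1% |
| 25% (target) | 14.3% | 2.7% | 7.4% |
| 40% (assumed) | 25.0% | 8.2% | 20.6% |

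**Step 3: size of the change.** Present ceiling = U dose / 3, so three infusions total the U dose. The alternative is the next lower listed dose / 3. For the dose column in which the Fibonacci scheme starts at level 3 (mg/kg):

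| Q3W dose declared U | Ceiling now (three-infusion total) | Ceiling without U doses (total) | Reduction |
|---|---|---|---|
| 0.030 | 0.010 (0.030) | 0.005 (0.015) | 50% |
| 0.060 | 0.020 (0.060) | 0.010 (0.030) | 50% |
| 0.100 | 0.033 (0.100) | 0.020 (0.060) | 40% |
| 0.150 | 0.050 (0.150) | 0.033 (0.100) | 33% |
| 0.200 | 0.067 (0.200) | 0.050 (0.150) | 25% |
| 0.267 | 0.089 (0.267) | 0.067 (0.200) | 25% |

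**Step 4: which dose columns count.** Below 0.060 mg/kg, the events that start the Fibonacci scheme are the same ones that open QW. In the column starting at level 1 the trigger has fired at 0.015, before all 8 later levels. In the column starting at level 2 it has fired by 0.030, before levels 3 to 8 (6 levels). For those 14 levels the gap needs QW dosing to be delayed while Q3W goes on to at least one further level, so they are left out. U at 0.030 is the same case in the level-2 and level-3 columns.

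**The case against.** The strongest reply is that the sentence is only an upper bound. It assigns no dose, Sections 2.1 and 2.2 leave room to start lower, and a toxic QW start would meet its own D or U decision within 2 to 4 patients. All of this stands and limits the weight of the point. It does not change the written limit, which takes no account of U.

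A second reply is that harm is not shown. A reader might infer that a QW start at the ceiling would be as toxic as the closed Q3W dose, since the 21-day totals match. The SAP does not support that: each infusion is one-third of the closed dose, and nothing in the document says DLTs follow the 21-day total. The QW DLT rate is unknown and may be lower.

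A reader might also infer that the ceiling contradicts the exclusion rule. It does not, because that rule bars only the U dose and higher doses.

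It can also be said that a first dose belongs to the protocol. The SAP states this rule itself, so its wording is open to comment.

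Finally, drawing the line at U is a choice: a dose with 2/3 or 2/4 DLTs is D and would still set the ceiling. U is used because it is the SAP's own line. Doses already tested may be given again unless they are U.

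**Conclusion.** The point stands as a small, optional improvement. As worded, a Q3W dose declared U before the first QW patient is dosed still sets the QW ceiling. This arises mainly when the triggering cohort itself reaches U. At a true DLT rate of 25% the bounds are 14.3%, 2.7% and 7.4% for cohorts of 2, 3 and 4, and the frequency is lower to the extent that QW is triggered by Grade 2 thrombocytopenia alone. In that event the present ceiling is higher than one based on the next lower dose, and excluding the U dose would reduce it by 25% to 50%.

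The frequencies assume a single cohort and a known true DLT rate. The reductions assume that the next lower listed dose was evaluated and is not U. Neither Table 1 nor the exclusion rules are called into question. Severity: consider.

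**What to change.** In SAP Section 2.2, add one clause to the end of the ceiling sentence: *that has not been declared U at the time the first QW patient is dosed*. Make the same change wherever the protocol carries this sentence.

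No extra clause is needed for U at the starting dose of 0.015 mg/kg, since Rule 1 in Section 4.2.1 already deals with a first dose that is too toxic.

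The change has no effect unless a Q3W dose is U before QW dosing starts. If that happens, the lower start may require one more QW cohort of 2 to 4 patients, within the Part 1 maximum of 70.
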